3. SURVEILLANCE PERIOD

Information will be collected for up to 5 years post procedure.

Annual reports will be submitted to the regulatory authority after marketing approval. Data will be collected until all patients complete 5-year follow-up, and application for use result evaluation will then be submitted.

Separately from the annual reports, frequency of ST will be reported as required.

Data will be collected at the following time points:

- Baseline (pre-procedure)
- Procedure
- Post-procedure to discharge
- 3 months (by visit preferred; by telephone is allowed) (Day 90 ± 14 days)
- 1 year (by visit preferred; by telephone is allowed) (Day 365 ± 28 days)
- 2 years (by visit or telephone) (Day 730 ± 28 days)
- 3 years (by visit or telephone) (Day 1095 ± 28 days)
- 4 years (by visit or telephone) (Day 1460 ± 28 days)
- 5 years (by visit or telephone) (Day 1825 ± 28 days)

Scheduled imaging follow-up is not required for this surveillance. If any imaging is performed as site standard practice, the imaging modality and results should be recorded in case report forms. In addition, if any imaging is performed for diagnosis, these should also be recorded in case report forms.

4. TREATMENT OF PATIENTS

Absorb GT1 will be implanted per optimal technique recommended by Abbott Vascular Japan Co., Ltd. Physicians should refer to the warnings, contraindications, and precautions in the most current version of product IFU for optimal treatment of each patient.

Physician will make final decision on antiplatelet therapy. However, product IFU of the Absorb GT1 BVS recommends dual antiplatelet therapy (DAPT) for at least 12 months. However, severe adverse device effect of very late stent thrombosis for more than one year after implantation was reported. Therefore, scheduled follow-up should be performed depending on the patient's condition and necessity of extending antiplatelet therapy should be considered with paying attention to the risk of adverse reactions such as bleeding, patient's background information, and anatomic features of the lesions. In addition to that, physician should also pay full attention to the increasing risk of bleeding due to the combination with anticoagulants. Physician should refer to the most current version of ADP antagonist IFU before treatment of each patient. Laboratory tests and clinical observation required for evaluating adverse reactions to ADP antagonists should be performed per the product IFU.

5. INFORMATION TO BE COLLECTED FOR THE SURVEILLANCE

5.1 Patient Baseline Information

- 1) Rave System Information
- 2) Registration Information
- 3) Demography
- 4) Ischemic Status and Other Cardiac Complications
- 5) Risk Factors and Comorbidities
- 6) Pre-procedural Laboratory Tests (If done, cardiac enzyme to be captured in cardiac enzyme form)
- 7) Pre-procedural Antiplatelet Medications

5.2 Procedural Information

- 1) Basic Procedural Information
- 2) Treated Lesion Information (Per lesion, stenting procedure only. Bifurcation lesion should be regarded as two lesions if both stented)
- 3) Pre-dilatation/Preparation (to be generated per dilatation/preparation)
- 4) Stenting Information (Including attempted but not implanted, to be generated per stent)
- 5) Post-dilatation (to be generated per dilatation)
- 6) Final Results

5.3 Pre- and Post-procedural Cardiac Enzymes**5.4 Procedural Complications****5.5 Antiplatelet Medications after the Procedure****5.6 Other Medications (Pre/Post-procedure)****5.7 Clinical Follow-up****5.8 Imaging Follow-up (target lesion only)**

- 1) Primary imaging modality
- 2) If MSCT/MRA, Restenosis assessment
- 3) CAG
- 4) Intravascular imaging

5.9 Device Malfunction/Deficiency**5.10 Scaffold/Stent Thrombosis****5.11 Adverse Event Other Than ST (to be reported)**

- Coronary Adverse events
 - Ischemia (Angina or ischemic test)
 - Diagnostic Catheter
 - Revascularization
- Bleeding
- Other serious adverse events (including adverse events related to antiplatelet medications)*
- Any adverse events related to Absorb GT1, or their causal relationship is "unknown"

*a serious adverse event: led to death, resulted in a life-threatening illness or injury, requires inpatient hospitalization or prolongation of existing hospitalization for treatment, impairment (e.g. resulted in a permanent impairment of a body structure or a body function) or threatened to impairment, led to a congenital abnormality or birth defect, an important medical event that may not result above but may be considered serious based upon the investigator's appropriate judgment.

For the adverse events described above, the causal relationship with the device or the procedure, adverse events related to antiplatelet medications, and outcomes of every adverse event should be recorded. For serious adverse events, reasons for the judgment of seriousness should be recorded as well.

5.12 Additional Treatment (If done with Absorb GT1)

If Absorb GT1 is used for treatment in the registered patients before starting commercial use (i.e., before ST rate through 3 months is available for all the registered patients, as primary endpoint), the information should be recorded.

- 1) Type
- 2) Basic Procedural Information
- 3) Treated Lesion Information (Per lesion, stenting procedure only. Bifurcation lesion should be regarded as two lesions if both stented)
- 4) Pre-dilatation/Preparation (to be generated per dilatation/preparation)
- 5) Stenting Information (Including attempted but not implanted, to be generated per stent)
- 6) Post-dilatation (to be generated per dilatation)
- 7) Final Results

6. ENDPOINTS

6.1 Primary Endpoints

- Scaffold thrombosis (Phase-1 + Phase 2 all patients with Absorb GT1):
 - If ST rate at 3 months is $\leq 0.9\%$, commercial sale will be started.
 - If ST rate at 2 years is $\geq 1.5\%$, investigation will be implemented to identify the cause.
- Exclusion of very small vessels
 - For Phase-1 patients only
- Scaffold apposition assessed by intravascular imaging:
 - For Phase-1 patients only
- Device deficiency at procedure of implantation (all patients)

6.2 Other Endpoints

To be evaluated per typical DES clinical studies.

6.2.1 Clinical Endpoints

- Component endpoints
 - Death (Cardiac/Vascular/Non-Cardiovascular)
 - Myocardial Infarction (TV-MI/NTV-MI)
 - Target Lesion Revascularization (ID-TLR/NID-TLR)
 - Target Vessel Revascularization (ID-TVR/NID-TVR)
 - All coronary revascularization
- Composite endpoints
 - DMR (All death/All MI/All revascularization)
 - TVF (Cardiac death/All MI/ID-TVR)
 - MACE (Cardiac death/All MI/ID-TLR)
 - TLF (Cardiac death/TV-MI/ID-TLR)
 - Cardiac death/All MI

6.2.2 Angiographic Endpoints (core lab analysis)

Include the following:

- Pre-procedure
 - Morphology
 - TIMI blood flow
 - Lesion length
 - Proximal RVD
 - Distal RVD
 - MLD
 - %DS
- Post-procedure
 - TIMI blood flow
 - Proximal RVD
 - Distal RVD
 - MLD (in-stent/in-segment)
 - %DS (in-stent/in-segment)
 - Acute gain (in-stent/in-segment)

6.2.3 IVUS/OCT Endpoints (core lab analysis)

Include the following:

- Pre-procedure (or after pre-dilatation)
 - Lumen diameter or Lumen area (proximal/distal)
- Post-procedure
 - Lumen diameter or Lumen area (proximal/distal)
 - MLA
 - Incomplete apposition of the Absorb BVS strut
 - Fracture of the Absorb BVS strut

7. ANALYSIS AND REPORTING

7.1 Adverse Event Reporting

When the Surveillance Site obtains the information on occurrence of the following events, capture the information to the case recording form in principle within 48 hours.

- ST or events possibly considered as scaffold or stent thrombosis
- adverse events to be reported, described in Section 5.11
- device malfunction or deficiency

Adjudication of deaths, MIs, and STs is performed by clinical events committee or scaffold thrombosis image-review committee. Surveillance sites will cooperate in providing images and relevant materials for adjudication to the Sponsor.

7.2 Angiographic Core Laboratory

For Phase-1 patients, QCA assessments of baseline and post-procedure angiograms and lesion morphology will be performed also by the angiographic core lab as well as by Surveillance Sites.

In case of ST, angiograms at baseline, procedure and the event will be analyzed by the angiographic core lab.

The Sponsor may request Surveillance Sites for angiograms for any purpose other than the above. Surveillance sites will cooperate in providing the angiograms to the Sponsor, if requested.

[REDACTED]

[REDACTED]

7.3 Intravascular Imaging

For Phase-1 patients, intravascular (IVUS/OCT) assessments will be performed by the respective core lab.

In case of ST, IVUS/OCT images at baseline, procedure and the event will be analyzed by the respective core lab.

The Sponsor may request Surveillance Sites for IVUS/OCT images for any purpose other than the above. Surveillance sites will cooperate in providing the IVUS/OCT images to the Sponsor, if requested.

7.4 Scaffold Thrombosis Image-Review Committee

Scaffold thrombosis events occurred during the Surveillance will be adjudicated by a scaffold thrombosis image-review committee. The committee will evaluate events reported by Surveillance Sites as scaffold thrombosis as outlined below:

- **Purpose**

To minimize risk of scaffold thrombosis by informing Surveillance Sites of result of investigation of scaffold thrombosis events occurred during the Surveillance based on all images, patient background information, and other relevant information concerning the events used to assess relationship to Absorb GT1 and complexity of lesions and to identify cause of scaffold thrombosis. Therefore, Surveillance sites will provide the information to the Sponsor as requested.

- **Member Selection**

In cooperation with CVIT, five (5) physicians who are well experienced with Absorb GT1 implantation or intravascular imaging will be selected in advance. Review committee meetings will require attendance of at least three (3) members. One (1) representative of Abbott Vascular may (not mandatory) attend the meetings or may present their opinion in advance. Physicians from relevant core labs may attend meetings or present their opinion depending on individual cases.

- **Review Method**

By teleconference or physical meeting.

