IVUS/OCT images taken during procedure will be sent immediately to the core lab, which will analyze the images and give feedback to the site as required. Images of ST, if occurred, will also be sent to the core lab.
 - All core labs will be those located in Japan in order to fulfill the goals mentioned above.

[figure not shown]
Phase 2 (All- patients):

- Until 2000 patients are registered (up to 200 sites)
 - Surveillance sites:
 - Phase 1 sites
 - Sites which have a physician accredited by CVIT, and experience of \geq 100 PCI cases per year.

- Main Purpose: To confirm safety
- Lesions to be treated: Per product IFU unless otherwise instructed
- To be treated by site standard procedure (imaging-guided implantation technique using IVUS/OCT recommended per product IFU)
- Primary Endpoint: ST through 3 months
 - Criteria: ST rate (in 2,000 patients: sum of Phase 1 and Phase 2)
 - ≤ 18 patients (0.9%): To start commercial sale
 - ≥ 19 patients: To investigate the cause and take appropriate actions
- All images of ST, if occurred, will be sent to the core lab.
- At Phase 2, IVUS/OCT images post procedure may be analyzed in the core lab as well. Surveillance sites will cooperate to the Sponsor, if requested.

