ATTACHMENT 2: DEFINITION IN THE SURVEILLANCE**Scaffold/Stent Thrombosis**

The definition of ARC will be used. The scaffold thrombosis image-review committee will adjudicate scaffold/stent thrombosis reported from the Surveillance Site based on this definition.

Scaffold/Stent thrombosis should be reported as a cumulative value at the different time points and with the different separate time points. Time 0 is defined as the time point after the guiding catheter has been removed and the subject left the catheterization lab.

- **Timing:**

- Acute scaffold/stent thrombosis*: 0 - 24 hours post stent implantation
- Subacute scaffold/stent thrombosis*: >24 hours - 30 days post stent implantation
- Late scaffold/stent thrombosis†: 30 days - 1 year post stent implantation
- Very late scaffold/stent thrombosis†: >1 year post stent implantation

*Acute/subacute can also be replaced by early scaffold/stent thrombosis. Early scaffold/stent thrombosis (0 - 30 days) - this definition is currently used in the community.

†Including “primary” as well as “secondary” late scaffold/stent thrombosis; “secondary” late scaffold/stent thrombosis is a scaffold/stent thrombosis after a target segment revascularization.

- **Categories:**

- Definite
- Probable

Definitions of each category are as follows.

- **Definite scaffold/stent thrombosis**

Definite scaffold/stent thrombosis is considered to have occurred by either angiographic or pathologic confirmation.

Angiographic confirmation of scaffold/stent thrombosis*

The presence of a thrombus† that originates in the scaffold/stent or in the segment 5 mm proximal or distal to the scaffold/stent and presence of at least one of the following criteria within a 48-hour time window:

- Acute onset of ischemic symptoms at rest
- New ischemic ECG changes that suggest acute ischemia
- Typical elevation or depression in cardiac biomarkers (refer to definition of spontaneous MI)

- Nonocclusive thrombosis
 - Intracoronary thrombus is defined as a (spheric, ovoid, or irregular) noncalcified filling defect or lucency surrounded by contrast material (on 3 sides or within a coronary stenosis) seen in multiple projections, or persistence of contrast material within the lumen, or a visible embolization of intraluminal material downstream.
- Occlusive thrombus
 - TIMI 0 or TIMI 1 in- scaffold/stent or proximal to a scaffold/stent up to the most adjacent proximal side branch or main branch (if originates from the side branch).

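### Section 7.4 lets a sponsor representative attend, or give an opinion in advance to, the committee that classifies scaffold thrombosis, and does not separate that input from the classification behind the 18/19 sale criterion

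*Protocol*

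**What the plan says.** Protocol Section 7.4 gives the endpoint to one body: "Scaffold thrombosis events occurred during the Surveillance will be adjudicated by a scaffold thrombosis image-review committee". Attachment 2 confirms that this body applies the ARC definition: "The scaffold thrombosis image-review committee will adjudicate scaffold/stent thrombosis reported from the Surveillance Site based on this definition".

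On membership, Section 7.4 states: "In cooperation with CVIT, five (5) physicians who are well experienced with Absorb GT1 implantation or intravascular imaging will be selected in advance". On quorum: "Review committee meetings will require attendance of at least three (3) members". It then adds that one representative of the company "may (not mandatory) attend the meetings or may present their opinion in advance". The representative is mentioned apart from the five physicians and is given no vote. Core-lab physicians may also attend or give a view, case by case. The committee's stated purpose is to find causes and inform the sites, yet the same section assigns it the adjudication.

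The result has a direct consequence. Section 2.4, Phase 2, sets the criterion on the 2,000 patients of both phases: "≤ 18 patients (0.9%): To start commercial sale". At 19 or more, the cause is investigated and appropriate action taken. Section 6.1 and SAP Section 1.3.1 add a 2-year trigger at 1.5%. Attachment 2 makes ARC definite or probable ST the principal definition.

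**The concern.** The company whose launch depends on the count may give its view to the people who make the count, before they make it. Sponsor input is reasonable for cause-finding. For classification it is a possible route to bias, and Section 7.4 does not confine the input to the first task. The visible text states no voting rule, conflict-of-interest rule, closed session or masking to the running ST count.

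The opening matters most for probable ST. Attachment 2 rests that category on an unexplained early death, or on a myocardial infarction (MI) in the stented territory with no angiographic confirmation and no other evident cause. Both call for judgement, and in the second the images help least. At stake are the 3-month sale criterion, the 2-year rate, and how far a reader can rely on either as free of sponsor influence.

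**Working it through.** **1. The plan's own figure.** Protocol Section 2.4 gives 18 patients as 0.9% of 2,000.
- 18 / 2,000 = 0.900%: sale starts.
- 19 / 2,000 = 0.950%: investigation.

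The figure reproduces. Adjacent counts lead to different actions.

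**2. When one event matters.** Removing one event turns investigation into sale only when the count is exactly 19. For n patients and true 3-month rate p, the binomial gives

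P(X = 19) = C(n, 19) × p^19 × (1 − p)^(n − 19), with n = 2,000.

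The visible text gives no expected ST rate (the basis of the sample size in SAP Section 1.5 is redacted), so p is an assumption shown over a range. The last column is the chance of starting sale if one event were always removed, that is, if the limit were in effect 19.

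| Assumed true rate | P(exactly 19) | P(18 or fewer) | P(19 or fewer) |
|---|---|---|---|
| 0.5% | 0.4% | 99.3% | 99.7% |
| 0.7% | 4.1% | 88.3% | 92.4% |
| 0.9% | 8.9% | 56.2% | 65.1% |
| 1.0% | 8.9% | 38.1% | 47.0% |
| 1.2% | 5.2% | 12.7% | 17.9% |
| 1.5% | 0.9% | 1.2% | 2.1% |

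Example at 0.9%: 56.2% + 8.9% = 65.1%. The sensitivity is greatest when the true rate is close to the threshold and small well away from it.

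**3. Denominator.** SAP Section 2.1.2 counts only patients who had ST or were followed through the time point. With 1,980 evaluable patients (an illustration), 18 / 1,980 = 0.909%, which exceeds 0.9%, while 17 / 1,980 = 0.859%. The boundary count may therefore fall below 18. It remains a one-patient boundary.

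**4. The 2-year trigger.** With all 2,000 evaluable, 0.015 × 2,000 = 30 patients, so 29 (1.45%) does not trigger investigation and 30 (1.50%) does. The same adjudication feeds this figure.

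**5. Is sponsor input kept apart from classification?** Section 7.4 assigns adjudication, lists the cause-finding purpose and admits the representative, all for the same committee and the same meetings. Neither it nor Attachment 2 orders the steps. An opinion given in advance necessarily reaches the committee before it meets to classify the event.

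**The case against.** The strongest reply is that the plan already has substantial safeguards, and most of it stands.

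- **Review is not absent.** A reader might infer that the count is settled without independent review. The documents do not support that. Five physicians chosen with CVIT adjudicate and at least three must attend. For angiography, "In case of ST, angiograms at baseline, procedure and the event will be analyzed by the angiographic core lab", and Section 7.3 says the same for IVUS/OCT. The documents do not state that the members are free of ties to the sponsor, but they do describe review by people other than the sponsor.
- **Other inputs are checked.** Under Section 7.5 a separate clinical events committee evaluates deaths and suspected MIs, and no sponsor attendance is described for it. Attachment 2 treats a death as cardiac unless a non-cardiac cause is unequivocal. This narrows the room for influence, although the ST classification stays with the image-review committee.
- **One event seldom decides.** A reader might infer that a single reclassification decides commercial sale. It changes the action only at the boundary, and 19 or more leads to investigation, not to refusal of sale.
- **No bias is shown.** The probabilities describe how sensitive the rule is. The documents give no fraction of events that would be downgraded, so any figure for the resulting bias would follow from an invented input.
- **Core labs are a different case.** It is tempting to hold back all outside input until after classification. Definite ST depends on angiographic or pathological confirmation, so withholding core-lab readings would weaken the classification and remove a non-sponsor check.
- **A charter may exist** outside these documents and may already settle the matter.

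What remains is that an opinion can influence a judgement without a vote, and that the text expressly permits the opinion to come first.

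**Conclusion.** The point holds as a matter of governance. Section 7.4 contains an express permission, not merely a missing detail, and the visible text does not separate sponsor input from the ARC classification behind the 3-month criterion and the 2-year rate.

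Its size is limited. The chance that the count falls exactly where one removed event changes the 3-month action is about 9% if the true rate is 0.9% to 1.0%, about 4% to 5% at 0.7% or 1.2%, and below 1% at 0.5% or 1.5%. These figures assume 2,000 evaluable patients, independent events and a true rate that the visible text does not give. They say nothing about whether an event would in fact be reclassified. The finding is an avoidable opening in a count with consequences, and it should be closed before events are adjudicated.

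**What to change.** Amend Section 7.4, or cite a committee charter that already does the following:

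1. The physician members make and record the ARC classification of each event (definite, probable or not ST) in a session without the sponsor and before any sponsor opinion is given.
2. Core-lab readings are available to them at that session.
3. Sponsor input comes afterwards and only in the cause-finding discussion.
4. Only the classification recorded in step 1 feeds the 3-month count and the 2-year rate.
5. Reports show site-reported and adjudicated ST counts side by side, so that any reclassification is visible.

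The cost is wording in the protocol or charter and one extra line in the ST tables. No added patients, visits or data are needed. The downside is that the sponsor's technical input reaches the committee slightly later.

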7.5 Clinical Observation - Clinical Events Committee (CEC)

Clinical events committee (CEC) will evaluate all deaths and suspicion of MIs for 3 years maximally. Surveillance sites will cooperate in providing materials needed to adjudication (e.g., death report, discharged summary) to the Sponsor, if a patient is dead or is suspected to MI.

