If CK-MB is measured by Site-standards, the definition used in Absorb Japan clinical trial will be used. For other cases, use the Modified WHO definition.

Definition used in the Absorb Japan clinical trial
Classification and criteria of NQMI

Classification	Biomarker Criteria	Additional Criteria
Periprocedural PCI (≤48h post-PCI)	CK-MB >5 x URL	Baseline value* < URL
Periprocedural CABG (≤48h post-CABG)	CK-MB >10 x URL	Baseline value < URL, and any of the following: New pathologic Q waves** or LBBB; new native or graft vessel occlusion; imaging evidence of loss of viable myocardium
Spontaneous All late events that are not associated with a revascularization procedure will be considered simply as spontaneous.	CK-MB > URL, or Troponin*** > URL	One or more of the following must also be present: (a) symptoms of ischemia; (b) development of pathological Q waves** (c) ECG changes indicative of new ischemia - (new ST-T changes or new LBBB), (d) or imaging evidence of a new loss of viable myocardium or a new regional wall motion abnormality
Reinfarction (not related to procedure)	If the CK and CK-MB values are stable or decreasing on 2 samples, a 25% or greater increase 3 to 12 hours after second sample is required to diagnose recurrent MI.	If biomarkers are increasing or peak not reached then insufficient data to diagnose recurrent MI.

URL=Upper Reference Limit
 LBBB=Left Bundle-branch Block
 * Baseline biomarker value is required before study procedure and presumes a typical rise and fall post
 ** If abnormal Q-wave is observed, then adjudicated as Q-MI
 *** If both values are obtained, then CK-MB must be used for adjudication

Modified WHO definition

Elevation of CK > 2 x URL and CK-MB > URL without abnormal Q-wave.

Myocardial infarction - Relation to the Target Vessel

All infarcts that cannot be clearly attributed to a vessel other than the target vessel will be considered related to the target vessel.

Revascularization

The revascularizations in the Surveillance will be adjudicated by Sites per the ARC definition.

- **Location of Revascularization:**

- **Target Lesion Revascularization (TLR)**

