##### **1.3.2.1 Clinical Endpoints**

Clinical endpoints will be evaluated in hospital and at each follow-up time point (3 months, and 1, 2, 3, 4, and 5 years).

- Component endpoints
  - Death (Cardiac/Vascular/Non-Cardiovascular)
  - Myocardial Infarction (TV-MI/NTV-MI)
  - Target Lesion Revascularization (ID-TLR/NID-TLR)
  - Target Vessel Revascularization (ID-TVR/NID-TVR)
  - All coronary revascularization
- Composite endpoints
  - DMR (All death/All MI/All revascularization)
  - TVF (Cardiac death/All MI/ID-TVR)
  - MACE (Cardiac death/All MI/ID-TLR)
  - TLF (Cardiac death/TV-MI/ID-TLR)
  - Cardiac death/All MI

Clinical events committee (CEC) will evaluate all deaths and suspected of MIs for 3 years maximally. Surveillance sites will cooperate in providing materials needed to adjudication (e.g., death report, discharged summary) to the Sponsor, if a patient is dead or is suspected to have MI.

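### A silent CK-MB rise that meets the periprocedural MI definition reaches the CEC only if someone recognises it, so MI and its composites can be understated

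*Protocol*

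**What the plan says.** **Definition.** Attachment 2 of the protocol offers two biomarker definitions. "If CK-MB is measured by Site-standards, the definition used in Absorb Japan clinical trial will be used"; otherwise the Modified WHO definition applies (CK above 2 x URL and CK-MB above URL, without an abnormal Q wave). In the first, the periprocedural PCI row asks for CK-MB above 5 x URL within 48 hours and a baseline below URL, and nothing more.

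**Collection.** Protocol 5.3 lists "Pre- and Post-procedural Cardiac Enzymes" as a data item of its own.

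**Adjudication.** Protocol 7.5: "Clinical events committee (CEC) will evaluate all deaths and suspicion of MIs for 3 years maximally". Sites supply material "if a patient is dead or is suspected to MI". SAP 1.3.2.1 has the same trigger ("Clinical events committee (CEC) will evaluate all deaths and suspected of MIs for 3 years maximally"), with material sent "if a patient is dead or is suspected to have MI".

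**Reporting.** Protocol 7.1 sets 48-hour reporting for actual or possible scaffold thrombosis, device malfunction or deficiency, and "adverse events to be reported, described in Section 5.11". The coronary items in 5.11 are "Ischemia (Angina or ischemic test"), diagnostic catheter and revascularization. Section 5.11 also covers bleeding, other serious adverse events, and any event related to Absorb GT1 or of unknown relation. MI is not named.

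**The concern.** The definition and the trigger work on different information. The definition can be met by a laboratory value in a patient who feels well. The trigger needs somebody to suspect an infarction. Where a raised CK-MB was drawn and entered but nobody read it as an MI, no written step connects the entry to the committee that is meant to decide.

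Such a patient would be counted as free of MI. The event falls in the first 48 hours, so the omission carries into every cumulative MI rate from hospital to 5 years. With up to 200 sites in Phase 2, the same CK-MB value could be an adjudicated MI at one site and no event at another, which is what central adjudication is there to prevent. The reported rates could then disagree with the surveillance's own enzyme data under its own definition.

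**Working it through.** The plan states no MI rate to reproduce, so the check is mainly a comparison of the texts.

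1. **Can a silent event qualify?** Yes. In the NQMI table of Attachment 2, the CABG and spontaneous rows each require clinical, ECG or imaging evidence besides the biomarker. The PCI row requires only a baseline below URL.
2. **Are the values held?** Item 5.3 collects them. Only its heading is visible, so I assume that the form records CK-MB, the site's URL and the sampling time.
3. **Do the values lead to the CEC?** No such step is visible. Section 7.1 refers to 5.11 but not to 5.3 or to 5.4 (procedural complications). Sections 7.5 and SAP 1.3.2.1 do not say who raises suspicion or at what value. For thrombosis, 7.1 has low-threshold wording that takes in possible events; there is no equivalent for MI.
4. **Can 5.11 catch the event anyway?** Yes, through the serious-event item or the device-related/unknown item. Either way, someone must first recognise the rise as an adverse event and classify it. Under 7.6, events other than death, MI and scaffold thrombosis stay with the site.
5. **How is a missed event counted?** Under SAP 2.1.2, a patient with no recorded DMR event who is followed through the time point stays in the denominator as a non-event. Under SAP 2.1.3 such a patient is censored as event-free.
6. **Which endpoints?** All MI enters DMR, TVF, MACE and cardiac death/all MI; TV-MI enters TLF. Attachment 2 assigns an MI to the target vessel unless it is clearly due to another, so a missed periprocedural MI would usually count in TLF too.

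**Size, as illustration only.** Missed MIs = N x e x r x m, where N = 2,000 (protocol 2.3), e is the share of patients with usable paired enzymes, r the rate of silent qualifying values among them, and m the share not flagged. The documents give none of e, r or m. Setting e = 1 gives the largest value:

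| r (assumed) | m (assumed) | Patients missed | Percentage points |
|---|---|---|---|
| 0.5% | 25% | 2,000 x 0.005 x 0.25 = 2.5 | 0.125 |
| 1% | 50% | 2,000 x 0.01 x 0.50 = 10 | 0.5 |
| 2% | 50% | 2,000 x 0.02 x 0.50 = 20 | 1.0 |
| 3% | 50% | 2,000 x 0.03 x 0.50 = 30 | 1.5 |
| 5% | 100% | 2,000 x 0.05 x 1.00 = 100 | 5.0 |

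Each figure shrinks in proportion to e. For the composites these are upper bounds, because some of the patients will also have another component event.

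**The case against.** The best defence is that 7.5 is silent rather than restrictive. It does not say that only the site may suspect an MI. The sponsor holds the 5.3 values, and a result above the protocol's own threshold is an obvious ground for suspicion. Section 7.4, by contrast, expressly ties the thrombosis committee to events reported by sites. A screen could also sit in a CEC charter, a data-management plan or redacted text. This stands as far as it goes: the documents do not show that no screen exists, and a reader should not infer that review depends on the site alone. But a permitted screen is not a planned one, and nothing visible commits anyone to it.

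Four stronger readings are also tempting, and the documents do not support them:

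- *Enzyme-only MI is on no reporting list.* It is not named, but the 5.11 catch-alls can hold it once recognised.
- *A stated share of TLF or MACE is lost.* No MI or TLF rate is given. The eligible group is also smaller than 2,000, because the CK-MB definition applies where CK-MB is measured and requires a baseline below URL.
- *The loss is differential.* This is a single-arm surveillance. Ascertainment may vary between sites, but there is no comparator against which to bias a contrast.
- *The commercial-sale decision is affected.* That rests on scaffold thrombosis. Definite thrombosis needs angiographic or pathological confirmation, and the MI route to probable thrombosis needs documented acute ischemia in the stented territory. An isolated enzyme rise meets neither.

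**Conclusion.** The concern holds as a gap in the written ascertainment rule. A periprocedural MI can be established by values already entered, yet under the plan it reaches the CEC only if somebody recognises it. MI, TV-MI and the five composites can be understated, by an amount that depends on site practice. The direction is clear; the amount is not. Across the assumed inputs above it runs from about 2 to 100 patients, which shows only that the documents cannot settle it.

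The affected measures are all Other Endpoints with no decision threshold, and the 3-month and 2-year thrombosis criteria are not directly touched. The change should be made, but it does not put the main safety criterion in doubt. Enzymes that were never drawn are a separate gap. The conclusion assumes that no unseen operating document already screens the 5.3 values; if one does, a cross-reference to it would be enough.

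**What to change.** - **Protocol 7.5 and SAP 1.3.2.1:** send to the CEC every patient whose 5.3 values show CK-MB above 5 x URL within 48 hours after PCI with baseline below URL, whether or not the site suspected MI.
- **Where CK-MB is not routinely measured:** use CK above 2 x URL as the prompt for CEC review. A trigger copying the full Modified WHO rule would seldom fire there, because it also needs CK-MB. The CK value is only a prompt; the CEC still applies the definition.
- **Protocol 5.11:** add MI, including enzyme-only MI, as a named item, which brings it under 7.1.
- **Reporting:** give the number of patients with evaluable pre- and post-procedure enzymes beside the MI and composite rates, so that readers can see how many patients could have been classified.

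The cost is one edit check on an existing form, short text changes and some extra cases for the existing committee. The check can be run retrospectively on values already entered. Treatment, visits and sample size do not change. Reported MI and composite rates may rise.
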